# 4.6 Health Economic Outcomes

Additional exploratory analyses related to resource cost and utilization will be completed. Specifically, the analyses listed in **Table 9** will be conducted. Note that resource cost data will not be collected during Phase 1 of the study, so the analyses which relate to cost will only be conducted using Phase II data.

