	never) to 4 (extreme or always). A higher score indicates worse
	pain, stiffness, or functional limitation.
	The EuroQol-5 Dimensions
	The EuroQol-5 Dimensions (EQ-5D) is a validated instrument
	which assesses an individual's current health status and heath
	related quality of life. The EQ-5D-3L descriptive component
	assesses five dimensions: mobility, self-care, usual activities,
	pain/discomfort, and anxiety/depression over three levels of
	severity. The EQ visual analogue scale (EQ VAS) assesses the
	respondent's self-rated overall health state on a scale from 0 (worst
	imaginable health state) to 100 (best imaginable health state).
	Numeric Rating Scale
	The NRS is a validated measure of knee pain. The NRS is an 11
	point Likert type scale anchored by 0 "no pain" and 10 "worst
	possible pain". Subjects rate their average pain over the last 48
	hours.
	Patient Preference Questionnaire
	Patient preferences are concerned with determining patient-related
	factors such as patients' adherence to treatment, patients'

	satisfaction with treatment, and health outcomes. Patient
	preferences will be measured utilizing questions to elicit patients'
	preferences following their knee OA treatment.
	Resource Utilization and Costing
	Health economics will be evaluated throughout the study.
	Healthcare resource utilization for each subject will be recorded to
	capture information about healthcare costs following index
	treatment with nSTRIDE APS or HA and follow-up.
Imaging	Radiographs
Assessment	Standing posterior-anterior (PA) fixed flexion knee radiographs (X-
Tools:	rays) are used to assess structural features of the joint, including
	joint space width, and presence or absence of subchondral
	sclerosis, subchondral cysts, and osteophytes. X-ray assessments
	will be performed by a core imaging laboratory.
Primary Endpoint:	The primary endpoint will be the change in pain from baseline to 12
	months following injection of nSTRIDE APS or HA, as measured by
	the WOMAC LK 3.1 pain subscale.
Primary Hypothesis	H ₀ : μ _{APS} = μ _{HA} vs H ₁ : μ _{APS} ≠ μ _{HA}
Primary Hypothesis for nSTRIDE	H ₀ : μ _{APS} = μ _{HA} vs H ₁ : μ _{APS} ≠ μ _{HA}
Primary Hypothesis for nSTRIDE Superiority Testing:	H ₀ : $\mu_{APS} = \mu_{HA} vs H_1: \mu_{APS} \neq \mu_{HA}$ Where:
Primary Hypothesis for nSTRIDE Superiority Testing:	H ₀ : $\mu_{APS} = \mu_{HA} vs H_1: \mu_{APS} \neq \mu_{HA}$ Where: H ₀ is the Null Hypothesis

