# Table 9 - Planned Phase II Statistical Analysis – Health Economic Outcomes

Predictor Variable	Outcome Variable(s)	Statistic	Expected Outcome	Time points
Treatment / Crossover Group	Difference in Quality- Adjusted Life Years (QALY)	One-Way Anova	Trend APS Superior	Time of initial treatment until "failure" or end of study (Phases I and II)
Treatment / Crossover Group	Mean monthly OA-related cost for help and/or transportation	One-Way Anova	Trend APS Superior	Phase II
Treatment / Crossover Group	Mean cost per 6 months for OA-related cost for medical and/or workplace- related cost	One-Way Anova	Trend APS Superior	Phase II
Treatment / Crossover Group	Improvement in Utility Score as measured by EQ-5D Δ Single Index Value	Repeated Measures ANOVA or Friedman Test	Trend APS Superior	Time of initial treatment until "failure" or end of study (Phases I and II)
Treatment/Cr ossover	Mean cost per 6 months for	One-Way Anova	Trend APS Superior	Phase I

Group	OA-related		
	cost for		
	restricted		
	medications		

At each follow-up visit, the quality-adjusted life years (QALYs) will be calculated by multiplying the duration of time to failure (i.e. rescue medication or procedure) by a health-related quality of life (HRQoL) weight (i.e. utility score) associated with that health state. Therefore, the two key elements— HRQoL and survival—are incorporated. The EQ-5D general health state rating (scored on a scale of 0 (worst imaginable health state) to 100 (best imaginable health state)) will be used as the HRQoL weights.

In addition, the analyses will include economic cost-benefit/cost-effectiveness analyses to measure and calculate the direct and indirect cost comparison between nSTRIDE and alternative treatment options. Zimmer Biomet will rely on publicly-available, standardized datasets, such as those available from the U.S. Department of Health & Human Services, the National Center for Health Statistics and the Bureau of Labor Statistics, when conducting these analyses to help ensure outcome validity and reproducibility.

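### SAP 4.6 restricts cost analyses to Phase II, but Table 9 contains a Phase I cost row, and the cost-effectiveness analysis has no stated horizon to align its costs with QALYs counted from injection

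*SAP*

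**What the plan says.** SAP section 4.6 commits to the analyses in Table 9 and then restricts them. On collection it says: "Note that resource cost data will not be collected during Phase 1 of the study". It draws from this the rule that every cost analysis is confined to data from the long-term phase. Table 9 is itself titled "Planned Phase II Statistical Analysis – Health Economic Outcomes".

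The rows of Table 9 do not all follow that rule:

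- **QALYs and EQ-5D utility gain** run from initial treatment to failure or "end of study (Phases I and II").
- **Help/transport cost** and **medical/workplace cost** are timed Phase II.
- **Restricted-medication cost per 6 months** has entries reading "One-Way Anova Trend APS Superior Phase I". Its predictor is Treatment/Crossover group, as in every other row.

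The text under Table 9 ends QALY time at failure, which it defines as rescue medication or a procedure. It then adds that "the analyses will include economic cost-benefit/cost-effectiveness analyses to measure and calculate the direct and indirect cost comparison" between nSTRIDE and alternative treatments, relying on public standardised datasets. It gives no time horizon, effect measure or list of cost components.

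The protocol synopsis, under Resource Utilization and Costing, says: "Health economics will be evaluated throughout the study". Its exploratory endpoints list resource utilization only at the long-term time points, months 12 to 60.

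**The concern.** There are two linked problems.

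The first is a plain contradiction. Section 4.6 rules out Phase I cost data and Phase I cost analysis, and the table it introduces contains a Phase I cost analysis. An analyst cannot follow both. The grouping in that row adds a difficulty: crossover is open to subjects only in months 12 to 60, so first-year cost would be compared across groups defined by a later choice. That is not a randomised comparison.

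The second is a gap. The effect measures start at injection and the main cost rows start at month 12, and nothing in the cost-effectiveness paragraph says how the two are to be aligned. If the Phase II rule is applied as written, the cost side omits the first year and the index injection, while the effect side includes whatever first-year QALY time precedes failure. Cost effectiveness is a stated aim of the long-term phase, and a ratio built that way would be hard to interpret.

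**Working it through.** The plan states no figure for this point, so there is nothing to reproduce. The check compares the texts and then makes one simple calculation.

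**Step 1: section 4.6 against the restricted-medication row.** There are two possible readings.

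- Phase I in that row is a slip for Phase II. The row then agrees with section 4.6, but no cost row in Table 9 covers the first year.
- Phase I is intended, for example by pricing medication use recorded in that phase. The sentence in section 4.6 is then wrong for this row, and first-year cost consists of restricted medication alone.

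The text has to change under either reading.

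**Step 2: predictor against timing.** SAP section 1.2 and the protocol's Study Design and Procedures allow crossover only in the long-term phase. During Phase I every subject is in one of two randomised arms. The four Treatment/Crossover groups can be applied to Phase I cost only in retrospect.

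**Step 3: time spans.**

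| Table 9 item | Starts | Ends |
|---|---|---|
| QALY, utility | injection (month 0) | failure or end of study |
| Help/transport cost | month 12 | within Phase II |
| Medical/workplace cost | month 12 | within Phase II |
| Restricted-medication cost | Phase I as printed | Phase I as printed |

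**Step 4: share of effect time without matching cost.** Let T be the months from injection to failure or end of study. Phase II starts at month 12, so on the literal reading the share of QALY time with no cost data is min(T, 12) / T. Only T = 60 is the planned end of study; the other values are an assumed range.

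| T (months) | Calculation | Share without cost |
|---|---|---|
| 60 | 12/60 | 20% |
| 48 | 12/48 | 25% |
| 36 | 12/36 | 33% |
| 24 | 12/24 | 50% |
| 18 | 12/18 | 67% |
| 12 or less | T/T | 100% |

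Because failure includes rescue medication, early values of T are possible. The index injection, at time 0, lies before the Phase II cost period for every subject.

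**The case against.** The strongest reply is that the pairing in step 4 is never stated. The cost-effectiveness paragraph is introduced as an addition to Table 9. It names no ratio, and it relies on public datasets that might supply index-treatment or first-year costs. Section 4.6 speaks of cost data collected in the study, and the price of an assigned injection need not be collected from subjects. Table 9 tests QALYs and costs in separate rows, with costs as monthly or 6-monthly means. All of this is right. A reader might infer that the SAP has decided to set both-phase QALYs against Phase II costs, but the documents support only the narrower statement that the horizon and components are undefined and that the literal reading leads there.

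A reader might also infer that the protocol contradicts the Phase II rule. It does so weakly at most. The general sentence on health economics can be satisfied by EQ-5D collection throughout, and the protocol's objectives, design section and endpoint list, like SAP section 1, place cost work in the long-term phase.

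On grouping, the SAP applies Treatment/Crossover groups to first-year data elsewhere: Table 8 analyses WOMAC pain change from baseline to month 12 that way. So this is not a contradiction in itself. It remains a poor choice for a Phase I cost when the randomised arm is available.

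The analyses are also exploratory. That stands, and it sets the severity.

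**Conclusion.** The contradiction between section 4.6 and the Phase I row of Table 9 is explicit. So is the difference in time span between the QALY and utility rows and the two Phase II cost rows. The cost-effectiveness analysis is under-specified. On a literal reading, it would leave 20% of effect time without cost for a subject failure-free to month 60, and up to 100% for failure at or before month 12. These shares assume that the Phase II rule governs the cost-effectiveness analysis and that no external source fills the first year.

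Three stronger inferences are not supported:

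- **That one treatment is favoured.** The documents give no prices and no first-year resource use. A difference in index price could be offset by the other omitted costs, so the direction is unknown.
- **That the first year's benefit is always counted in full.** QALY time stops at failure, so it is counted in full only for subjects who have not failed by month 12.
- **That a known fraction of treatment cost or of subjects is affected.** No Table 9 row names study-treatment cost, so counting injections does not give a share of cost. The 15% to 25% attrition figures in the SAP are planning allowances, and nothing says how early leavers enter these analyses.

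The primary and secondary endpoints, alpha and sample size are unaffected. The severity is minor.

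**What to change.** 1. **Reconcile section 4.6 with the last row of Table 9.** If the Phase I row is intended, amend the sentence in section 4.6 so that it no longer excludes it, and analyse the row by randomised arm. If it is a slip for Phase II, correct the row.
2. **State one horizon, the effect measure and the cost components for the cost-effectiveness analysis.** There are two workable options:
   - Start costs at the index injection. Add a unit cost for the assigned treatment and its procedure for every injected subject, and declare the Phase I items left uncosted. Add Phase I medication cost only if the recorded data allow pricing. SAP section 2 promises a summary of restricted medication by type, and the documents supplied do not show that quantity is recorded.
   - Count a second QALY from month 12, use that one in any cost-effectiveness ratio, and label the result as Phase II only, excluding index treatment.

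The cost is SAP wording and, for the first option, unit prices applied to allocation and injection records. No new data collection is needed. The downside of the first option is that some Phase I resource use stays uncosted; the second gives up any statement about the index treatment.

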# Table 9 - Planned Phase II Statistical Analysis – Health Economic Outcomes

Predictor Variable	Outcome Variable(s)	Statistic	Expected Outcome	Time points
Treatment / Crossover Group	Difference in Quality- Adjusted Life Years (QALY)	One-Way Anova	Trend APS Superior	Time of initial treatment until "failure" or end of study (Phases I and II)
Treatment / Crossover Group	Mean monthly OA-related cost for help and/or transportation	One-Way Anova	Trend APS Superior	Phase II
Treatment / Crossover Group	Mean cost per 6 months for OA-related cost for medical and/or workplace- related cost	One-Way Anova	Trend APS Superior	Phase II
Treatment / Crossover Group	Improvement in Utility Score as measured by EQ-5D Δ Single Index Value	Repeated Measures ANOVA or Friedman Test	Trend APS Superior	Time of initial treatment until "failure" or end of study (Phases I and II)
Treatment/Cr ossover	Mean cost per 6 months for	One-Way Anova	Trend APS Superior	Phase I

Group	OA-related		
	cost for		
	restricted		
	medications		

At each follow-up visit, the quality-adjusted life years (QALYs) will be calculated by multiplying the duration of time to failure (i.e. rescue medication or procedure) by a health-related quality of life (HRQoL) weight (i.e. utility score) associated with that health state. Therefore, the two key elements— HRQoL and survival—are incorporated. The EQ-5D general health state rating (scored on a scale of 0 (worst imaginable health state) to 100 (best imaginable health state)) will be used as the HRQoL weights.

In addition, the analyses will include economic cost-benefit/cost-effectiveness analyses to measure and calculate the direct and indirect cost comparison between nSTRIDE and alternative treatment options. Zimmer Biomet will rely on publicly-available, standardized datasets, such as those available from the U.S. Department of Health & Human Services, the National Center for Health Statistics and the Bureau of Labor Statistics, when conducting these analyses to help ensure outcome validity and reproducibility.

Mean WOMAC Pain Δ (12 Month minus Baseline)Independent variables: Treatment, Subgroup, Treatment*Subgroup InteractionWOMAC MCID Function Responder rateIndependent variables: Treatment, Subgroup, Treatment*Subgroup InteractionWOMAC MCID Function Responder rateIndependent variables: Treatment, Subgroup, Treatment*Subgroup InteractionMean WOMAC Function Δ (12 Month minus Baseline)Independent variables: Treatment*Subgroup InteractionMean WOMAC Function Δ (12 Month minus Baseline)Independent variables: Treatment, Subgroup, Treatment*Subgroup InteractionOMERACT-OARSI Responder / Non-responder (12 Month)Independent variables: Treatment*Subgroup InteractionMean WOMAC Pain Δ (12 Month minus Baseline) in K-L II SubgroupIndependent variables: Treatment, Subgroup, InteractionMean WOMAC Pain Δ (12 Month minus Baseline) in K-L II SubgroupIndependent variables: Treatment, Subgroup, InteractionMean WOMAC Pain Δ (12 Month minus Baseline) in K-L II SubgroupIndependent variables: Treatment, Subgroup, Interaction
(12 Month minus Baseline)Independent variables: Treatment, Subgroup, Treatment*Subgroup InteractionWOMAC MCID Function Responder rateIndependent variables: Treatment, Subgroup, Treatment*Subgroup InteractionMean WOMAC Function Δ (12 Month minus Baseline)Independent variables: Treatment, Subgroup, Treatment*Subgroup InteractionOMERACT-OARSI Responder / Non-responder (12 Month)Independent variables: Treatment*Subgroup InteractionMean WOMAC Pain Δ (12 Month minus Baseline)Independent variables: Treatment*Subgroup InteractionOMERACT-OARSI Responder / Non-responder (12 Month)Independent variables: Treatment*Subgroup InteractionMean WOMAC Pain Δ (12 Month minus Baseline) in K-L II SubgroupIndependent variables: Treatment, Subgroup, Treatment, Subgroup,
Baseline)Treatment, Subgroup, Treatment*Subgroup InteractionWOMAC MCID Function Responder rateIndependent variables: Treatment, Subgroup, Treatment*Subgroup InteractionMean WOMAC Function ΔAnalysis of CovarianceMean WOMAC Function ΔIndependent variables: Treatment*Subgroup InteractionMean WOMAC Function ΔIndependent variables: Treatment*Subgroup InteractionMean WOMAC Function ΔIndependent variables: Treatment, Subgroup, Treatment, Subgroup, Treatment*Subgroup InteractionOMERACT-OARSI Responder / Non-responder (12 Month)Independent variables: Treatment*Subgroup InteractionMean WOMAC Pain Δ (12 Month minus Baseline) in K-L II SubgroupIndependent variables: Treatment, Subgroup, Treatment, Subgroup, Treatment, Subgroup, Treatment, Subgroup, Treatment, Subgroup, Treatment, Subgroup, Treatment, Subgroup, Treatment, Subgroup, Treatment*Subgroup,
Treatment*Subgroup InteractionWOMAC MCID Function Responder rateIndependent variables: Treatment, Subgroup, Treatment*Subgroup InteractionMean WOMAC Function ΔAnalysis of CovarianceMean WOMAC Function ΔIndependent variables: Treatment*Subgroup InteractionMean WOMAC Function ΔIndependent variables: Treatment*Subgroup InteractionMean WOMAC Function ΔIndependent variables: Treatment, Subgroup, Treatment, Subgroup, Treatment*Subgroup InteractionOMERACT-OARSI Responder / Non-responder (12 Month)Independent variables: Treatment*Subgroup InteractionMean WOMAC Pain Δ (12 Month minus Baseline) in K-L II SubgroupIndependent variables: Treatment, Subgroup, Treatment, Subgroup, Treatment*Subgroup Interaction
WOMAC MCID Function Responder rateIndependent variables: Treatment, Subgroup, Treatment*Subgroup InteractionMean WOMAC Function ΔAnalysis of CovarianceMean WOMAC Function ΔIndependent variables: Treatment, Subgroup, Treatment, Subgroup, Treatment, Subgroup, Treatment, Subgroup, Treatment, Subgroup, Treatment, Subgroup, Treatment*Subgroup InteractionOMERACT-OARSI Responder / Non-responder (12 Month)Independent variables: Treatment*Subgroup InteractionMean WOMAC Pain Δ (12 Month minus Baseline) in K-L II SubgroupIndependent variables: Treatment, Subgroup, Treatment, Subgroup, Subgroup, Treatment, Subgroup, Treatment, Subgroup, Treatment, Subgroup, Treatment, Subgroup, Treatment, Subgroup,
WOMAC MCID Function Responder rateIndependent variables: Treatment, Subgroup, Treatment*Subgroup InteractionMean WOMAC Function ΔAnalysis of CovarianceMean WOMAC Function ΔIndependent variables: Treatment, Subgroup, Treatment, Subgroup, Treatment*Subgroup Interaction0OMERACT-OARSI Responder / Non-responder (12 Month)Mean WOMAC Pain Δ (12 Month minus Baseline) in K-L II SubgroupIndependent variables: Treatment*Subgroup InteractionMean WOMAC Pain Δ (12 Month minus Baseline) in K-L II SubgroupIndependent variables: Treatment, Subgroup, Treatment, Subgroup, Treatment*Subgroup Interaction
Responder rateIndependent variables: Treatment, Subgroup, Treatment*Subgroup InteractionMean WOMAC Function ΔAnalysis of CovarianceMean WOMAC Function ΔIndependent variables: Treatment, Subgroup, Treatment, Subgroup, Treatment*Subgroup Interaction0OMERACT-OARSI Responder / Non-responder (12 Month)Mean WOMAC Pain Δ (12 Month minus Baseline) in K-L II SubgroupIndependent variables: Treatment*Subgroup InteractionMean WOMAC Pain Δ (12 Month minus Baseline) in K-L II SubgroupIndependent variables: Treatment, Subgroup, Treatment, Subgroup, Treatment Subgroup Interaction
Treatment, Subgroup, Treatment*Subgroup InteractionMean WOMAC Function ΔAnalysis of Covariance(12 Month minus Baseline)Independent variables: Treatment, Subgroup, Treatment*Subgroup InteractionOMERACT-OARSI Responder / Non-responder (12 Month)Independent variables: Treatment, Subgroup, Treatment, Subgroup, Treatment*Subgroup Interaction
Mean WOMAC Function ΔAnalysis of Covariance(12 Month minus Baseline)Independent variables: Treatment, Subgroup, Treatment*Subgroup InteractionOMERACT-OARSI Responder / Non-responder (12 Month)Independent variables: Logistic RegressionMean WOMAC Pain Δ (12 Month minus Baseline) in K-L II SubgroupIndependent variables: Treatment*Subgroup InteractionMean WOMAC Pain Δ (12 Month minus Baseline) in K-L II SubgroupIndependent variables: Treatment*Subgroup InteractionMean WOMAC Pain Δ (12 Month minus Baseline) in K-L II SubgroupIndependent variables: Treatment, Subgroup, Treatment, Subgroup, Treatment, Subgroup, Treatment*Subgroup Interaction
Mean WOMAC Function ΔAnalysis of CovarianceΔIndependent variables: Treatment, Subgroup, Treatment*Subgroup Interaction(12 Month minus Baseline)Independent variables: Treatment*Subgroup InteractionOMERACT-OARSI Responder / Non-responder (12 Month)Independent variables: Treatment, Subgroup, Treatment, Subgroup, Treatment*Subgroup InteractionMean WOMAC Pain Δ (12 Month minus Baseline) in K-L II SubgroupIndependent variables: Treatment, Subgroup, Treatment, Subgroup, Treatment, Subgroup, Treatment, Subgroup, Treatment, Subgroup, Treatment, Subgroup, Treatment, Subgroup, Treatment, Subgroup, Treatment, Subgroup, Treatment*Subgroup Interaction
Δ (12 Month minus Baseline)Independent variables: Treatment, Subgroup, Treatment*Subgroup InteractionOMERACT-OARSI Responder / Non-responder (12 Month)Logistic RegressionMean WOMAC Pain Δ (12 Month minus Baseline) in K-L II SubgroupIndependent variables: Treatment*Subgroup InteractionMean WOMAC Pain Δ (12 Month minus Baseline) in K-L II SubgroupIndependent variables: Treatment, Subgroup, Treatment, Subgroup, Treatment, Subgroup, Treatment, Subgroup, Treatment, Subgroup, Treatment, Subgroup, Treatment, Subgroup, Treatment*Subgroup Interaction
(12 Month minus Baseline)Treatment, Subgroup, Treatment*Subgroup InteractionOMERACT-OARSI Responder / Non-responder (12 Month)Logistic RegressionMean WOMAC Pain Δ (12 Month minus Baseline) in K-L II SubgroupIndependent variables: Treatment*Subgroup InteractionMean WOMAC Pain Δ (12 Month minus Baseline) in K-L II SubgroupIndependent variables: Treatment, Subgroup, Treatment, Subgroup, Treatment, Subgroup, Treatment, Subgroup, Treatment*Subgroup Interaction
Baseline)Treatment*Subgroup InteractionOMERACT-OARSI Responder / Non-responder (12 Month)Logistic RegressionIndependent variables: Treatment, Subgroup, Treatment*Subgroup InteractionMean WOMAC Pain Δ (12 Month minus Baseline) in K-L II SubgroupIndependent variables: Treatment *Subgroup InteractionMean WOMAC Pain Δ (12 Month minus Baseline) in K-L II SubgroupIndependent variables: Treatment, Subgroup, Treatment *Subgroup Interaction
OMERACT-OARSI Responder / Non-responder (12 Month)Logistic RegressionIndependent variables: Treatment, Subgroup, Treatment*Subgroup InteractionMean WOMAC Pain Δ (12 Month minus Baseline) in K-L II SubgroupIndependent variables: Analysis of CovarianceIndependent variables: Treatment*Subgroup InteractionMean WOMAC Pain Δ (12 Month minus Baseline) in K-L II SubgroupIndependent variables: Treatment, Subgroup, Treatment*Subgroup Interaction
OMERACT-OARST Responder / Non-responder (12 Month)Independent variables: Treatment, Subgroup, Treatment*Subgroup InteractionMean WOMAC Pain Δ (12 Month minus Baseline) in K-L II SubgroupIndependent variables: Treatment variables: Treatment, Subgroup, Treatment, Subgroup, Treatment*Subgroup Interaction
Responder / Non-responder (12 Month)Independent variables: Treatment, Subgroup, Treatment*Subgroup InteractionMean WOMAC Pain Δ (12 Month minus Baseline) in K-L II SubgroupIndependent variables: Treatment, Subgroup, Treatment, Subgroup, Treatment*Subgroup Interaction
Non-responder (12 Month)       Treatment, Subgroup, Treatment, Subgroup, Treatment*Subgroup Interaction         Mean WOMAC Pain Δ (12 Month minus Baseline) in K-L II Subgroup       Analysis of Covariance         Independent variables: Treatment, Subgroup, Treatment, Subgroup, Treatment*Subgroup Interaction
Month     Treatment*Subgroup Interaction       Mean WOMAC Pain Δ (12 Month minus Baseline) in K-L II Subgroup     Analysis of Covariance       Independent variables: Treatment, Subgroup, Treatment*Subgroup Interaction
Mean WOMAC Pain Δ (12 Month minus Baseline) in K-L II SubgroupAnalysis of CovarianceIndependent variables: Treatment, Subgroup, Treatment*Subgroup Interaction
(12 Month minus Baseline) in K-L II Subgroup Treatment, Subgroup, Treatment*Subgroup Interaction
(12 Month Hinds       Independent variables:         Baseline) in K-L II       Treatment, Subgroup,         Subgroup       Treatment*Subgroup Interaction
Baseline) In K-L II     Treatment, Subgroup,       Subgroup     Treatment*Subgroup Interaction
Treatment*Subgroup Interaction
Mean WOMAC Function Analysis of Covariance
(12 Month minus
(12 Month minus independent variables.
Baseline) III N-L II Treatment*Subgroup Interaction
Analysis of Coverience
Analysis of Covariance
(12  Month minus)
(12 Month Innus Independent Valiables. Baseline) Treatment Subgroup
Treatment*Subgroup Interaction

